## **10. STATISTICAL CONSIDERATIONS**

### **10.1. Study Endpoints**

#### **10.1.1. Primary Efficacy Endpoint**

The primary end-point of the study is progression free survival 12 weeks after start of therapy, measured as a binary variable. This will be based on the disease evaluation performed 12 weeks after start of treatment with central radiology review. Patients who are alive and progression free at this time will be considered as successes. Patients who have progressed or are dead at this time will be considered as failure. Patients with an unknown progression status will be considered as failure. The diagnosis of progression should be based on tumor measurements, according to the RECIST 1.1 criteria.

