### **5.6.3. After End of Treatment:**

End of treatment Visit (to be performed 28 days after end of treatment): Physical exam (with Blood pressure assessment and vital and cancer signs and symptoms), clinical laboratory test, ECG, adverse events.

After discontinuation of protocol treatment in patients who have not progressed, will still be re-evaluated by imaging every 8 weeks, unless they have started a new anti-cancer therapy.

After progression disease: follow up for survival, patient status (alive/dead/lost to follow up) and new anti-cancer therapy.

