**5.9. Central Images Review**

All images assessments will be central reviewed through on-line platform by:

[Redacted]

It is strongly recommended to upload the baseline MRI/CT scan before patient inclusion, if it is not possible, it should be done as soon as possible after patient inclusion.

All images assessments, performed during the clinical trial, should be uploaded to the specific platform as soon as possible.

[figure not shown]
All scans generated should be exportable in electronic format (DICOM) to enable secure and rapid electronic transmission to the designated central imaging laboratory.

All scans will be identified *only* by the specific codification detailed in the radiologic guidelines.

A central review report will be generated as per specific form.

For any issue regarding central images review, please contact to:

[Redacted]

An additional document will be provided in the Investigator Site File with detailed central images review loading information.

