### **10.4. Sample Size and Statistical analysis**

The drug will be separately investigated in the following liposarcoma subtypes:

- Well-differentiated liposarcoma/dedifferentiated liposarcoma (ALT-WD)
- Myxoid/round cell liposarcoma.

The Simon two-stage design will be separately applied in each stratum. A total of 17 patients will be included in each stratum for the first step of the trial. For the second step, 20 (up to 37) additional patients will enter in each stratum provided the results of the first step were positive. A total of 37 patients could enter the study in each stratum.

Success will be defined as documented disease stabilization or response after at least 12 weeks of therapy.

The following design characteristics and decision rules apply separately to each stratum. The Simon optimal one sample two stages testing procedure (optimal design) will be used with the following hypotheses:

- Success in 20% of the cases or less in one of the strata will be considered as unacceptable, and would not warrant further investigation (null hypothesis). Therefore, the value of P0 will be taken as 20%.
- Success in 40% of the cases or more in one of the strata will be considered as an acceptable result warranting further investigation of the drug in this histology (alternative hypothesis). Therefore, the value of P1 will be taken as 40%.

These two reference values are based on a retrospective analysis of the EORTC STBSG database of patients treated with 2nd line therapy.

Under those hypotheses, a total of 37 eligible and treated patients will need to be recruited in each stratum and followed for at least 12 weeks. The size of the type I and type II errors is 10% ( $\alpha=\beta=0.1$ ).

A total of 17 eligible and treated patients will be included (in each stratum) in the first step of the study.

1. If  $\leq 3$  successes are observed in a stratum, the trial will be stopped in this stratum with the conclusion that the drug should not be further investigated in this histology.
2. Else, patients will continue to be accrued until 37 eligible patients have been recruited and have started therapy. If 11 or more successes are observed in those 37 patients, we will conclude that the results of this trial warrant further investigation in this histology.

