2.6. EFFICACY: MAIN ENDPOINT

Following the instructions of the protocol primary efficacy endpoints in populations ITT and PP will be calculated following the criteria:

Patients who are alive and without evidence of progression at this time will be considered successes, and those who have progressed or died at this time will be considered treatment failures. Patients in whom progression is unknown or not available will also be considered failures. Diagnosis of progression should be based on measurements of tumor lesions, according to the RECIST 1.1 criteria.

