2.6.3. BASED ON CENTRALIZED ASSESSMENTS. ITT

The tables below will record the **response at 6 and 12 weeks**, based on **centralized assessments** TAC. As for the local evaluations. The centralized evaluations will be reviewed following the criteria specified in the protocol for the evaluation of the main endpoint:

"Patients who are alive and without evidence of progression at this time will be considered as successes, and those who have progressed or died at this time will be considered as treatment failures. Patients in whom it is unknown whether or not there is progression will also be considered as failures. "

In the **ITT population**, both 6 and 12 weeks.

Table 44. Response to treatment: Value. Centralized at 6 and 12 weeks ITT

		Cohort A	Cohort B	Total	p-value
		N (% , 95% CI)	N (% , 95% CI)	N (% , 95% CI)	
Response at 6 weeks	PD				
	SD				
	PR				
	Total				
Response at 12 weeks	PD				
	SD				
	PR				
	Total				

1: Chi-square; 2: Fisher's exact test

Responses will be recoded according to **clinical benefit (CR, RP or EE)** and in the ITT population.

Table 45. Clinical benefit, response to treatment: Value. centralized at 6 and 12 weeks ITT

		Cohort A	Cohort B	Total	p-value
		N (% , 95% CI)	N (% , 95% CI)	N (% , 95% CI)	
Response at 6 weeks	Yes				
	No (PD)				
	Total				
Response at 12 weeks	Yes				
	No (PD)				
	Total				

1: Chi-square; 2: Fisher's exact test

GEIS-30 STUDY

Statistical analysis plan

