2.7.3 PFS. CENTRAL ASSESSMENT. ITT

To describe the event in PFS, the protocol will be followed:

“Overall progression-free survival will be calculated from the date of initiation of treatment to the first date of documented progression or date of death, whatever the cause. Live patients with no evidence of progression at the time of analysis will be censored on the date of the last follow-up. ”

Table 56. Progression-free survival at 12 and 24 weeks according to cohorts (Central assessment. ITT)

Progression-free survival	N events	N patients at risk	% Estimated cumulative survival ratio	95% CI		
at 12 weeks	Cohort A					
	Cohort B					
at 24 weeks	Cohort A					
	Cohort B					
	Strategy	N (%) events	Median (weeks)	Min-Max	Standard error	p-value ¹
Progression-free survival	A					
	B					
	Total					

1: Log-rank test

Figure 3. Progression-free survival according to cohorts (Central assessment ITT). Kaplan-Meier curve.

GEIS-30 STUDY

Statistical analysis plan

Table 57. Progression during follow-up (Central assessment. ITT)

	Cohort A		Cohort B		Total	p-value
	N (% , 95% CI)		N (% , 95% CI)		N (% , 95% CI)	
Progression-free survival	PD					
	Alive: Free of progression					
	Total					

1: Pearson Chi-square; 2: Fisher's exact test

Table 58. Time to PD (weeks) (Central assessment. ITT)

	Cohort A			Cohort B			Total		p-value ¹
	N	Mean (SD)	Median (Min-Max)	N	Mean (SD)	Median (Min-Max)	N	Mean (SD)	
Time to PD (weeks)									

1: Mann-Whitney U test

Table 59. Follow-up time (weeks) (Central assessment. ITT)

	Cohort A			Cohort B			Total		p-value ¹
	N	Mean (SD)	Median (Min-Max)	N	Mean (SD)	Median (Min-Max)	N	Mean (SD)	
Follow-up time (weeks)									

1: Mann-WhitneyU test

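### A week-7 local progression that central review does not confirm is a failure in the central 12-week rate but progression-free in central PFS, and no rule covers it

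*Protocol*

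**What the plan says.** **Endpoint.** Protocol 10.1.1 defines a binary week-12 status: "This will be based on the disease evaluation performed 12 weeks after start of treatment with central radiology review". It adds: "Patients with an unknown progression status will be considered as failure". SAP 2.6 repeats the rule ("Patients in whom progression is unknown or not available will also be considered failures"), and SAP 2.6.3 applies it to the central read ("Patients in whom it is unknown whether or not there is progression will also be considered as failures"). Protocol 10.4 words success differently: "Success will be defined as documented disease stabilization or response after at least 12 weeks of therapy".

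**End of imaging.** The notes to Table 5 (section 8.1) and Table 7 (section 8.2) run tumour assessment up to documented progression; Table 7 also ends it at death or new anti-cancer treatment. Neither names the assessor. Protocol 5.6.3 says: "After discontinuation of protocol treatment in patients who have not progressed, will still be re-evaluated by imaging every 8 weeks", unless new therapy has begun; sections 5.7 and 10.2 agree. After progression, 5.6.3 lists only survival, patient status and new therapy. Section 6.3.1 ends study drug at RECIST 1.1 progression and mentions no central confirmation.

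**Central review.** Protocol 5.9 says: "All images assessments, performed during the clinical trial, should be uploaded to the specific platform as soon as possible". A report is generated, but no turnaround time is set, and the section does not say that the report goes back to the site or decides whether scanning continues. Central pathology (5.3), by contrast, has a turnaround of about a week, a report to sites and a gatekeeping role.

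**PFS.** Protocol 10.1.2 counts progression or death from any cause as an event. SAP 2.7.3 follows it for central PFS: "Live patients with no evidence of progression at the time of analysis will be censored on the date of the last follow-up".

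**The concern.** One reader in effect ends imaging and another scores the endpoint, and the plan has no rule for disagreement. With no central step before drug and scanning stop, the decision at week 7 will in practice rest on the local reading.

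Two results are affected. The primary 12-week rate can lose patients whom central review never saw progress, which costs power and raises the chance of closing a cohort at stage 1. Central PFS can gain time during which nobody was looking at the tumour. The two central results then move apart, and the planned tables would not show why.

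**Working it through.** **1. One patient through the plan.** Take local progression at week 7 (day 50), a central read of stable disease on the same scan, and the patient alive beyond week 12. For illustration, let death come at 8 months, the approximate median survival after second-line chemotherapy quoted in Protocol 4.1 (8 × 365.25 / 12 / 7 = 34.8 weeks).

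| Analysis | How this patient appears |
|---|---|
| Central 12-week rate (SAP Table 45; Table 47 if in PP) | Failure. The only non-success row is No (PD), so the patient is shown as progressed |
| Local PFS (Tables 48, 52) | Event at week 7 |
| Central PFS (Tables 56, 60) | Progression-free at 12 and 24 weeks; event at death, week 34.8. If alive at analysis, censored at last follow-up |

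Table 45 counts the patient as a failure at week 12, while Table 56 counts the same patient as progression-free at week 12.

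**2. Direction of the PFS error.** Continued central reading would have dated progression at or before death or last contact. The planned rule uses death or last contact, so for these patients it can only leave central PFS time unchanged or lengthen it. Counting the local call as an event on its date gives the other extreme. The two analyses bracket the answer.

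**3. Would the tables reveal it?** Tables 50 and 54 break down types of progression and censoring for local PFS only. Central Tables 57 and 61 show only progressed versus alive and progression-free. Nothing cross-classifies the two readings.

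**4. The plan's design, reproduced.** Inputs from Protocol 10.4: p0 = 0.20, p1 = 0.40, both error rates 10%, stop at 3 or fewer successes in 17, positive at 11 or more in 37. With X1 ~ Bin(17, p) and X2 ~ Bin(20, p):

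P(positive | p) = Σ (k = 4 to 17) P(X1 = k) × P(X2 ≥ 11 − k)

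This gives 0.0948 at p = 0.20 and 0.9033 at p = 0.40. An exhaustive search for the Simon optimal design with these inputs returns the same 3/17 and 10/37. The stated design is correct.

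**5. Effect of lost successes.** Let d be the share of patients truly progression-free by central review at week 12 who are scored as failures because a local call ended imaging. The observable rate is p × (1 − d); for example 0.40 × 0.95 = 0.38 and 0.20 × 0.95 = 0.19. The documents do not give d, so the values are assumed.

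| d | Observable p1 | Power | Stage-1 stop when true rate is 40% | Observable p0 | Type I error |
|---|---|---|---|---|---|
| 0% | 0.40 | 90.3% | 4.6% | 0.20 | 0.0948 |
| 5% | 0.38 | 85.8% | 6.5% | 0.19 | 0.0705 |
| 10% | 0.36 | 79.9% | 8.9% | 0.18 | 0.0508 |
| 15% | 0.34 | 72.6% | 11.9% | 0.17 | 0.0353 |

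d is not the local-central discordance rate at week 7. A discordant patient who would have progressed centrally by week 12 is correctly a failure and costs nothing.

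**The case against.** - **Scoring unknown as failure is prespecified and conservative.** This stands. The rule cannot create a false positive, and type I error falls with power. The cost is lost power and an endpoint stricter than the one described.
- **A reader might infer that such a patient is censored in central PFS on the date of the local call, making this classic informative censoring.** The documents do not support that. Censoring is at last follow-up, survival follow-up continues after progression (Protocol 5.6.3 and 8.2), and any death is an event. Many such patients would probably be events at death. The bias comes from counting unscanned time as progression-free.
- **A reader might also infer that the protocol makes the site's declaration the end of imaging.** It names no assessor. The local reading is the practical inference, and the radiologic guidelines and Investigator Site File document mentioned in 5.9 are not available to check. The supportable defect is that the assessor is unnamed and no confirmation step is written down.
- **Local and central results are already reported side by side, and local PFS counts these calls as events.** True, and it gives partial protection. But separate tables do not identify the discordant patients, and local PFS also changes the dating for everyone else.
- **Extending imaging may not recover the lost successes.** This stands in part. A patient off drug since week 7 may not meet the 10.4 wording even with a stable week-12 scan, and one who has started new therapy would remain unknown. A return to 90.3% power should not be promised.

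**Conclusion.** The gap is real and the plan does not address it. A local-only progression at week 7 is a failure in the central 12-week rate and remains progression-free in central PFS until death or last follow-up. Central PFS is biased upward by an amount that cannot be estimated from the documents. The primary decision is affected conservatively: with an assumed 5% to 15% of true successes lost, power is 85.8% to 72.6% against the planned 90%, and type I error drops below its 9.5% attained value. Even the 5% case exceeds the stated 10% type II error (100 − 85.8 = 14.2%). All of this rests on the assumed share and on local readings ending imaging in practice. The sample size calculation itself is sound.

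**What to change.** **SAP 2.6.3–2.6.4 and 2.7.3–2.7.4.**
- List, by cohort, every local progression not confirmed centrally.
- In the central 12-week tables, show not evaluable centrally on a separate line from progressed, still scoring it as failure.
- Add a sensitivity analysis of central PFS that counts a local progression not confirmed centrally as an event on its date.

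These use data already collected and cost one listing, one table row and one analysis.

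**Protocol 5.6.3, 5.7, Table 5, Table 7 and 10.2.** State whose reading ends imaging. Where feasible, keep the week-12 scan for patients whose local progression is not confirmed centrally and who have not started new anti-cancer therapy. The cost is a few additional scans and earlier central reads of scans called progressed, which is a new operational step.

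**Protocol 10.1.1 and 10.4.** Reconcile status 12 weeks after starting treatment with success after at least 12 weeks of therapy, so that the scoring of a patient off drug at week 12 is defined. This is a wording change.

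These changes concern imaging, scoring and analysis only. They do not address treatment decisions.

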#### **10.1.2. Secondary Endpoints**

##### **Overall progression free survival (median PFS)**

Overall progression free survival will be computed from the date of start of treatment to the first documented date of progression or the date of death, whatever the cause. Patients alive and free from progression at the time of the analysis will be censored at the date of last follow-up.

##### **Objective tumor response**

Objective tumor response, measured according to the RECIST 1.1 criteria, will be used as secondary end-point in this trial.

Response criteria are essentially based on a set of measurable lesions identified at baseline as target lesions, and followed until disease progression.

##### **Time to onset of response**

It will be computed from the date of start of treatment to the time of first documented response.

##### **Duration of response**

It will be computed from time of attaining response to the time of first documented progression or death.

##### **Overall survival (OS)**

It will be computed from the date of start of treatment to the date of death, whatever the cause. Patients alive or lost for follow-up at the time of the analysis will be censored at the date of last follow-up.

##### **Clinical benefit rate**

Patients who achieve CR, PR, or SD for 6 months or more and an improvement of symptoms will be considered as having derived clinical benefit.

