### **5.6.1. Before treatment:**

Informed consent must be obtained prior to start of the specified screening window. Procedures conducted as part of the subject's routine clinical management (e.g., blood count, imaging study such as bone scan) and obtained prior to signing of informed consent may be utilized for screening or baseline purposes provided these procedures are conducted as specified in the protocol.

Screening: To determine patient eligibility, within 14 days prior treatment start, it should be performed the following assessments: consent form signature, inclusion/exclusion criteria, medical history, physical exam (with Blood pressure assessment and vital and cancer signs and symptoms), ECOG, concomitant medication, clinical laboratory test, ECG, LVEF (MUGA ECO), Baseline imaging CT/MRI, tumor specimen collection, serum collection.

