### **6.1. Inclusion Criteria**

A subject will be considered eligible for inclusion in this study if all the following criteria are met:

1. Subjects must provide written informed consent prior to performance of study-specific procedures or assessments and must be willing to comply with treatment and follow-up.
  - Informed consent must be obtained prior to start of the specified screening window.
  - Procedures conducted as part of the subject's routine clinical management (e.g., blood count, imaging study such as bone scan) and obtained prior to signing of informed consent may be utilized for screening or baseline purposes provided these procedures are conducted as specified in the protocol.
2. Age  $\geq$  18 years or legal age of consent if greater than 18 years
3. Histological confirmed diagnosis of high or intermediate grade malignant liposarcoma with metastatic or locally advanced disease. Formaline fixed paraffin embedded tumour block and/or representative H/E (haematoxylin/eosin) slides must be available for central pathologic review to classify tumors in the 2 eligible subtypes:
  - Well-differentiated liposarcoma/de-differentiated liposarcoma (ALT-WD)
  - Myxoid/round cell liposarcoma
4. Patient must have documentation of disease progression within 6 months prior to study entry.
5. Eastern Cooperative Oncology Group (ECOG) performance status of 0-1.
6. Measurable disease by RECIST v1.1 criteria. At least one measurable lesion located outside of a previously irradiated area. If the only measurable lesion is in a previously irradiated area, RECIST progression should be documented after radiotherapy, in the previous 6 months before study entry.

7. The patient should not be considered eligible for surgery or radical radiotherapy. e.g. Patients to whom surgery/radiotherapy cannot be performed with a curative intent due to the extension of the disease. In the case of radiotherapy, it may also be limited due to a previous treatment with radiotherapy in the same area.
8. The patient must have either been considered ineligible for systemic chemotherapy or received at least one previous regimen for relapsed, refractory or metastatic disease. A maximum of three previous lines for advanced/metastatic disease are allowed.

Patients not eligible for systemic chemotherapy:

- Because of age, a biological condition or patient-refusal

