## TABLE Of ASSESSMENT

	Before Treatment	During Treatment											After treatment		
		Week 0	W1	W3	W5	W7	W9	W 12	Every 4 weeks (after w12)	Every 8 weeks	Every 12 weeks	28 days after end of treatment	Before PD, every 8 weeks until PD	After PD every 12 weeks	
		Day 1	Day 8	Day 22	Day 36	Day 50	Day 64	Day 85							
Informed Consent	X														
Inclusion/Exclusion Criteria	X														
Medical history	X														
Physical Exam a (with vital and cancer signs and symptoms)	X	X	X	X	X	X	X	X	X	X		X	X		
ECOG	X	X	X	X	X	X	X	X	X	X			X		
Concomitant Medication	X	X	X	X	X	X	X	X	X	X					
Clinical Laboratory Tests b,c	X	X	X	X	X	X	X	X	X	X		X			
ECG d	X					X		X		X		X			
LVEF (MUGA/ECO)	X **							X				X			
Efficacy Assessment (Imaging/MRI) *	X **					X		X		X			X		
Adverse Events			X	X	X	X	X	X	X	X		X			
Tumor specimen collection 	X														
Serum collection 	X			X											
Treatment control and dispensing		X		X	X	X	X	X	X	X					
Survival															

\*Tumor assessment should be repeated in week 7 and week 12 and every 8 weeks thereafter until documented progression for patients with CR, PR, or SD and/or for patients who have discontinued study therapy due to toxicity or reasons other than progressive disease, unless they have started a new anti-cancer therapy.

\*\*Both tumor assessment before treatment and LVEF can be done up to 28 days prior the start of the treatment.

 Tumor sample will be collected before treatment.

Serum will be collected as described:

1. Within 72 hours prior starting the treatment (basal).
2. Within 72 hours after first 3 weeks of treatment (day 22).
3. Within 72 hours after radiological response is documented.
4. Within 72 hours after progressive disease is documented.

 Monitoring of BP: A measurement of BP should be taken the day of the visit +/- 3 days.

 Hematology Profile and Chemistry Profile (including liver Function) in every visit

 Thyroid function test (T4 and TSH):basal and every 12 weeks.

 ECG: Baseline, week 7 and 12 and every 8 weeks thereafter.

Unless otherwise indicated, during treatment the marge for visits / explorations is +/- 4 days and after completion of treatment +/- 7 days

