### **4. Physical Exam:**

**4.1 Pre-treatment (Screening):** Evaluation by body system, height, weight, body surface area (BSA) and measurement of vital signs (blood pressure and body temperature).

**4.2 During treatment and follow up visits:** Evaluation by body system, weight, body surface area (BSA) and verification of patient blood pressure measurements, every treatment visit before study drug administration and at every visit and follow-up visit.

**5. ECOG Performance Status (PS):** PS will be assessed at screening, at day 1 before the study drug is administered, and in week 1, 3, 5, 7, 9 and week 12. Thereafter, every treatment visit before the study drug is administered (4 weeks).

If subjects discontinue study treatment without disease progression (e.g., withdrawal of study treatment due to unacceptable toxicity), continue the assessments of ECOG PS in accordance with the disease assessments until subjects experience disease progression.

**6. Concomitant Medication:** The use of any natural/ herbal products or others “folk remedies” should be discouraged but use of these products, as well as use of vitamins or nutritional supplements and all others concomitant medications must be recorded in the Case Report Form (CRF). Any medications, with the exception noted in the section (additional details), which are considered necessary for patient’s welfare, and which it is believed will not interfere with the study medication, may be given at the discretion of the Investigator, providing the medication, doses, dates and reasons for administration in the CRF.

**7. Adverse Events:** The CTC-AE version 4.0 will be used to evaluate the clinical safety of the treatment in this study. Subjects will be assessed for AEs at each clinical visit and as necessary throughout the study.

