### **10.3. Safety assessment**

Any patient included in the study receiving at least a single dose of study medication will be evaluable for the toxicity analysis.

Safety profile will be characterized by treatment-emergent Adverse Events (TEAE), vital signs and laboratory abnormalities. Assessment of adverse events will include type, incidence, severity (graded by the National Cancer Institute [NCI] Common Terminology Criteria for Adverse Events [CTCAE], Version 4.0), timing, seriousness, and relatedness; and laboratory abnormalities. Baseline tumor-related signs and symptoms will be recorded as adverse events during the trial if they worsen in severity or increase in frequency.

In each study visit all adverse events will be registered according to NCI-CTC version 4.0

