1.16. OBJECTIVES OF THE STUDY

1.16.1. Primary objective

The objective of this study is to evaluate the activity of Pazopanib in patients with advanced and / or metastatic liposarcoma by means of progression-free survival (PFS) determined after 12 weeks of treatment (according to the RECIST criteria v1.1 and central radiological revision).

1.16.2. Secondary objectives:

- Median progression-free survival (median PFS).
- Objective tumor response [Complete confirmed response (CR) and partial response (PR) defined by RECIST 1.1].
- Time to start of response.
- Duration of response.
- Overall survival (OS).
- Clinical benefit rate (CBR).
- Growth modulation index (GMI).
- Security profile (according to CTCAE, version 4.0).

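### The protocol's clinical benefit rate contains a symptom clause that some eligible patients cannot meet and no defined measure supports, while the SAP tabulates a different endpoint under the same name

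*Protocol*

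**What the plan says.** **Protocol definition.** Section 10.1.2 (Clinical benefit rate) gives the condition as "CR, PR, or SD for 6 months or more and an improvement of symptoms will be considered as having derived clinical benefit". The rate is one of the eight secondary objectives in section 4.3.2. It has no target value, power statement or decision rule.

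**Who can enter.** Inclusion criterion 5 in section 6.1 asks for "Eastern Cooperative Oncology Group (ECOG) performance status of 0-1". No criterion requires tumour symptoms, and section 12.1 documents the qualifying progression by CT or MRI.

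**What is recorded about symptoms.**
- The physical examination row of the Table of Assessment (Table 5) is labelled "with vital and cancer signs and symptoms" and is marked at screening, at every treatment visit, 28 days after treatment and at follow-up before progression.
- Section 8.2, item 4.2, describes the on-treatment examination as "Evaluation by body system, weight, body surface area (BSA) and verification of patient blood pressure measurements". It names no symptom score.
- ECOG is assessed repeatedly (section 8.2, item 5) but is not tied to the clinical benefit rate.
- Section 10.3 states: "Baseline tumor-related signs and symptoms will be recorded as adverse events during the trial if they worsen in severity or increase in frequency".

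**SAP.** Section 1.16.2 keeps the rate among the secondary objectives. Sections 2.6.1 to 2.6.4 (Tables 41, 43, 45 and 47) then recode tumour response at weeks 6 and 12 into clinical benefit. Yes means CR, PR or SD (the last two appear under untranslated Spanish abbreviations), and No means PD. Appendix I (Tables 82 to 87) uses the same coding.

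**The concern.** There are two linked problems.

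First, the protocol makes benefit depend on symptoms getting better. A patient who had none at entry cannot meet that, however long the tumour is controlled. For a patient who did have symptoms, nothing says how much improvement counts, at which visit, on what scale or in whose judgement. A rate built this way mixes tumour control with the share of patients who happened to have symptoms at entry. If that share differs between the well-differentiated/dedifferentiated and the myxoid/round cell cohorts, their rates differ for reasons unrelated to the drug.

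Second, the SAP does not compute that endpoint. A reader who takes the SAP's clinical benefit tables as the protocol's secondary endpoint would be reading week 6 or week 12 disease control as six-month benefit with symptom relief.

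**Working it through.** **1. A figure to reproduce.** None is stated for this endpoint. The primary decision rule (stop at 3 or fewer of 17, positive at 11 or more of 37, with 20% against 40%) was recomputed as background. Exact type I error is 0.0948 and power 0.9033, in line with the stated 10% errors. That rule does not use the clinical benefit definition.

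**2. The two definitions side by side.**

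| Element | Protocol 10.1.2 | SAP 2.6.1–2.6.4 and Appendix I |
|---|---|---|
| Tumour status | CR, PR or SD | CR, PR or SD |
| Duration or time | 6 months or more | Status at week 6 and at week 12 |
| Symptoms | Improvement required | Not mentioned |
| Counted as No | Everyone else | PD |

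The SAP's efficacy tables, 40 to 73, are numbered without a gap, and none carries the protocol's definition.

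**3. How typical patients are classified.** The protocol sentence has two readings. On the literal reading the symptom condition covers CR, PR and SD. On the narrow reading both qualifiers belong to SD only.

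| Patient | Protocol, literal | Protocol, narrow | SAP, week 12 |
|---|---|---|---|
| No symptoms at entry, PR for one year | No | Yes | Yes |
| No symptoms at entry, SD for one year | No | No | Yes |
| Symptoms at entry, SD at week 12, PD at week 20 | No | No | Yes |
| Symptoms at entry that improve, SD for one year | Yes, if improvement is accepted | Yes, if improvement is accepted | Yes |

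The second row fails on either reading of the protocol. The third row shows that removing the symptom clause alone would not bring the documents together, because the duration also differs.

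**4. Can improvement be read from the scheduled data?** The examination note is unscored. The adverse-event rule records only deterioration. ECOG could show a change, but a patient at 0 cannot improve on it, and SAP Table 73 stops at week 12, short of six months. So no planned variable can be turned into improved, yes or no, by a stated rule.

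**5. Size under the literal reading.** Let d be the share with disease control for at least six months, a the share of those patients without symptoms at entry, and i the share of the symptomatic ones who improve. Then

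rate = d × (1 − a) × i, with ceiling d × (1 − a) when i = 1.

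None of d, a or i is in the documents. All are assumed, and using the entry share for a assumes that symptom status is independent of disease control.

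| d | a = 20% | a = 40% | a = 60% |
|---|---|---|---|
| 20% | 16% | 12% | 8% |
| 30% | 24% | 18% | 12% |
| 40% | 32% | 24% | 16% |

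At d = 30% in a full cohort of 37, 37 × 0.30 = 11.1 patients have disease control. The ceilings are 37 × 0.24 = 8.9, 37 × 0.18 = 6.7 and 37 × 0.12 = 4.4 patients. If only half of the symptomatic patients improve (i = 0.5), the rates become 12%, 9% and 6%. On the narrow reading the reduction applies only to the SD part of d. If asymptomatic patients are over-represented among those with disease control, the ceiling is lower than shown; if under-represented, it is higher.

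**The case against.** Four stronger conclusions are tempting, and the documents support none of them.

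- **That asymptomatic patients with long disease control will be reported as having no benefit.** This follows from the protocol sentence but not from the planned tables. The SAP scores any CR, PR or SD as Yes, and its between-cohort p-values use that symptom-free coding.
- **That symptoms are not scheduled for recording.** They are, within the physical examination, at screening and throughout. What is missing is a scale, a threshold and a link to the endpoint.
- **That a one-year partial response without symptoms certainly fails.** The sentence can be read with both qualifiers on SD alone, and such a patient then counts. Long SD without symptoms is still lost.
- **That the 24% to 12% ceilings are estimates for this trial.** They are arithmetic on assumed inputs. Nor does the symptom share replace drug effect: it sets a ceiling, and the drug still determines disease control and improvement beneath it.

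Two further arguments deserve weight. Requiring symptom relief before speaking of clinical benefit is a defensible choice, but it then needs a measure and a population in which relief is possible. The SAP also reports Kaplan–Meier progression-free survival at 24 weeks (Tables 48, 52, 56 and 60), which is close to six-month disease control. That is useful information, but it is a survival estimate with censoring, not the per-patient rate that the protocol defines.

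**Conclusion.** The concern holds in two parts. The protocol's clinical benefit rate contains a clause that eligible patients without symptoms cannot meet (certainly those with SD, and on the literal reading those with CR or PR too), and no rule is given for judging it in the others. The SAP retains the objective by name but tabulates disease control at weeks 6 and 12, so the protocol's endpoint is not produced and a different one carries its name.

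The mismatch rests on the text alone. The numerical loss under the protocol wording depends on an unknown share of asymptomatic patients. With 30% disease control and 20% to 60% asymptomatic, independent of disease control, the ceiling falls from 30% to between 24% and 12%. The consequence is confined to one secondary endpoint; the primary endpoint and its stopping and success rules are unaffected. It should be corrected because the endpoint cannot be reproduced as written.

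**What to change.** 1. Use one definition in Protocol 10.1.2 and in the SAP: CR, PR or SD lasting at least the protocol's six months by RECIST 1.1, with no symptom clause. Word it so that it is clear whether the duration applies to all three categories or to SD only.
2. Add a SAP table of this rate with its confidence interval, per cohort. Scans are planned at week 12 and every 8 weeks after, so at weeks 20 and 28, while six months is about week 26. A note to the table should say which scan establishes the duration.
3. Rename Tables 41, 43, 45 and 47, and the corresponding rows of Tables 82 to 87, as disease control at the stated visit.
4. Report symptom improvement separately and descriptively, only among patients with tumour symptoms recorded at baseline.

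The cost is wording in both documents and one added efficacy table, using scans already scheduled. The downside is that the clinical benefit rate becomes a purely radiological measure; item 4 keeps the symptom information visible without letting it decide the rate.
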